Blinding – Statistician: The statistician involved in examining the effects of the conditions of primary and secondary outcomes will not be informed of participants’ specific intervention allocation. Condition allocated will be marked as “Condition A, Condition B, Condition C” to ensure the statistician remains blinded to participants’ intervention upon primary and secondary analysis of the results. All other potential markers of allocation will be removed from the data analysis file. Upon completion of these analyses, the statistician will be become unblinded when examining mediators and moderators as well as intervention completion rates, due to differences in the total number of modules/lessons across each condition. This data will only be reviewed by the trial statistician upon completion of the primary and secondary outcomes.

Blinding – Chief Investigators, Trial Manager and Research Officers/Assistants: The chief investigators, trial manager and research assistants will be unblinded to participants’ allocation as they will have access to the Black Dog Institute Research Engine to contact participants if they experience adverse events, and to provide support to participants allocated to the “guided use” condition. They will also be responsible for downloading and cleaning the data extract. The Chief Investigators, Trial Manager, and Research Officers/Assistants will not be involved in data analysis of the primary and secondary outcomes.

For the study outputs, a CONSORT flow diagram will be provided outlining study recruitment, including n for each stage.

8. Sample Size

The total baseline sample size required for detecting change in the primary outcome is 489. This is based on calculations using $\alpha=0.05$, power=0.8, small to medium effect sizes for psychoeducation ($d=0.10$), self-directed CBT ($d=0.35$), and guided CBT ($d=0.65$) on depressive outcomes at primary endpoint and a 20% attrition rate between baseline and primary endpoint.

Specifically, this sample size is comprised of the following sample sizes for each of the participant groups:

1. Trial Arm 1=163 participants
2. Trial Arm 2=163 participants
3. Trial Arm 3=163 participants.

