An additional study assessment will occur at follow-up, with the secondary endpoint assessed at 4-months post-baseline. At secondary endpoint, participants will be invited to complete the primary endpoint assessment via an automated email/SMS invitation generated by the Black Dog Institute Research Engine. The outcome measures assessed at primary endpoint are outlined in Appendix D. The primary endpoint assessment is entirely self-report. It will take approximately 20 minutes to complete and can be completed on any Internet-enabled device. Participants will have 7 days to complete the primary endpoint assessment (from invitation date) and will receive two reminders to complete the assessment (sent day 3 and day 5). Upon completion of the secondary endpoint assessment, trial participation will cease. Participants will be thanked for their time and provided with additional information on mental health and help-seeking resources.

Young people will be reimbursed for the time taken to complete the study assessments. Participants will be reimbursed \$10AUD (electronic gift voucher) for completion of the baseline, post-test and follow-up assessments. The total possible reimbursement will be \$30AUD, which will be emailed and sent via SMS to participants within 14 days of their completion of the scheduled assessment. These amounts are aligned with the best-practice wage-payment model (Dickert & Grady 1999) such that participants are paid for time taken to participate in the study, using the current minimum wage of \$19.84p/hr. In addition, participants allocated to trial arm 2 (guided use of ClearlyMe) will be reimbursed an additional 25AUD (GiftPay Voucher sent by email and SMS) upon randomisation to this group to cover the cost sending and receiving SMSs. This amount was based on the estimated costs of approximately 12 SMS sent per week at \$0.30 per message. Because of this incentive, data integrity checks will be embedded into the online assessments to check for duplicate users at baseline (e.g., emails, and mobile number checks) and to ensure that standards of internet studies are met (Reips, 2002).

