All study assessment data will be collected and stored on the Black Dog Institute Research Engine. This Research Engine stores data on secure servers commissioned by the University of New South Wales IT and is hosted on the GovDC Data Centres located in Silverwater, Sydney. The data is stored in a SQL Server 2016 database which is backed up daily on a drive on the server. The drive itself is backed up daily to a tertiary location. Server backups are performed daily and weekly. The daily backups are retained for 2 weeks, the weekly backups for 6 weeks, the monthly backups for 6 months and half yearly backups for 7 years. Access to the servers is strictly controlled and only authorised UNSW IT and Black Dog Institute IT staff can access the servers (VPN) using Two Factor Authentication. UNSW servers are penetration tested regularly for security vulnerabilities and UNSW IT also perform regular security patches and updates on the servers. The Research Engine itself is only accessible to authorised personnel using password protected accounts. For this project, only the Chief Investigator, researchers listed on this application, and the Black Dog Institute IT and data analytics team have access to the research data in the Research Engine. All data will be destroyed 15 years after the completion of the study by the Chief Investigator or Black Dog Institute IT.

The Research Engine automatically generates a unique participant identification code, which is included in all reports. This code enables de-identification of the dataset for analyses. For

analyses, all study assessment data will be exported, via a Microsoft Excel file, from the Research Engine to SPSS Version 26 for analysis by the research team. These files will be stored on UNSW OneDrive and only accessible to the Chief Investigators A and B, Trial Managers, Data Analyst and Senior Research Officer listed on the project. The Trial Manager and Senior Research Officer will de-identify the dataset (i.e., remove name, mobile phone number, email addresses, IP addresses, and free response data) and prepare it (i.e., cleaning and ensuring blinding) for the trial statistician to conduct the primary and secondary analyses. The de-identified and blinded file will then be transferred to the trial statistician for analyses using a password protected OneDrive file. Aggregate deidentified data in a password protected OneDrive file will be retained for future evidence synthesis.

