For participants allocated to trial arm 1 and 2, the study will also collect research data associated with their use of the intervention. This information will be used to determine which aspects of the intervention are important for improved outcomes. This trial will collect the following usage data from the *ClearlyMe* app: lessons completed, collections completed, features accessed, total time spent in app, content liked/disliked, content saved, and individual responses to lesson activities. This data will be extracted automatically from individuals' smartphones and transferred via the Internet to the Black Dog Institute Research Engine. This data will then be available for download (similar to the study assessment data) via the Black Dog Research Engine, connected to participants' study assessments using their unique participant identification code. Participants responses will be analysed to determine their compliance and engagement with the content, including linguistic analysis of their free responses. For participants allocated to trial arm 3 (i.e., the control condition), the study will also collect research data on the number of times each participant accesses each psychoeducation flyer via the URLs in the weekly SMSs. The time and date of access will be included.

For the risk management protocol, a report will be generated from the Black Dog Institute Research Engine that contains only participants' contact details (mobile phone number, email), name and age. This file will be password protected, stored on the UNSW OneDrive and only accessible by the Trial Manager, for conduct of any of the risk management telephone calls that are required during the study.

For participants allocated to Trial Arm 2, a report will be generated from the Black Dog Institute Research Engine that contains their mobile phone number, name and age. This file will be used to conduct the weekly SMS chats. This file will be password protected, stored on the UNSW OneDrive and only accessible to the research team members conducting the weekly SMS chats.

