Procedure for the type and duration of the follow-up of subjects after adverse events

The current trial will recruit participants from a clinical population, it's expected that feelings of anxiety and/or depression, and suicidal thoughts or thoughts of self-harm will be common. Included at the end of each mental health assessment at (baseline, primary or secondary endpoint) are suggested resources and contact details for services, should participants become distressed and need assistance. These services include Lifeline, Beyond Blue, and Kids Helpline as well as a range of resources and support from the Black Dog Institutes website. Participants that experience an AE related to severe suicide ideation or severe depressive symptom will be offered a follow-up call from a Clinical Psychologist. The Clinical Psychologist will conduct a brief risk assessment over the phone to determine the level of risk. If determined to be at risk, the participant will be advised to contact an appropriate service (e.g., a GP, the BDI Psychology Clinic, Mental Health Hotline). If the risk of harm is deemed significant enough to break confidentiality, or the participant requests it, their parents will be contacted by mobile telephone within an additional two working days. Referral suggestions will be provided.

Procedure for accounting for missing, unused, and spurious data

All data will be collected via online surveys, rather than pencil-and-paper responses, reducing the amount of missing data or errors within the data set. To maintain data integrity frequency tables of all variables (including time and date information) will be collected and checked to ensure that scale items have only legal values. These legal values will also be checked for coherency (i.e., do end times/dates occur after corresponding 'start' time/dates).

Any missing items will be flagged with a value that cannot be confused as a legal value. Additionally, a present/absent indicator variable will be created for each data collection timepoint to track missing data due to participant absence. For partially answered inventories, respondents that answer at least 50% of items on a scale and still have a valid score will be allowed (Bell & Fairclough, 2014). Respondents that have less than 50% of items on scale completed will be assigned as missing values. The research team will be guided by the trial statistician in data analysis.

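### Staff who know the allocation clean the outcome data and mask the arms before the file reaches the statistician, so the statistician's blinding does not cover cleaning decisions

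*Protocol*

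**What the plan says.** Protocol Section 7 (Trial Design) has separate blinding paragraphs for the statistician and for the trial team. The statistician receives arms coded A, B and C, with other markers of allocation removed from the analysis file. For the team it says: "The chief investigators, trial manager and research assistants will be unblinded to participants’ allocation". The stated reasons are contact about adverse events and support for the guided arm. It then says of the same people: "They will also be responsible for downloading and cleaning the data extract". The one restriction on them is that they take no part in analysing the primary and secondary outcomes.

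Section 10 (Treatment of Subjects) describes the handover: "The Trial Manager and Senior Research Officer will de-identify the dataset" and "prepare it (i.e., cleaning and ensuring blinding) for the trial statistician to conduct the primary and secondary analyses". The file is then transferred to the statistician. The same section says a contact-details report is "only accessible by the Trial Manager, for conduct of any of the risk management telephone calls", which places the Trial Manager in the safety-call process.

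Appendix J, on missing, unused and spurious data, sets checks for legal values and coherent dates. For incomplete scales, "respondents that answer at least 50% of items on a scale and still have a valid score will be allowed"; below that threshold the scale is set to missing.

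**The concern.** Blinding a statistician protects choices made from the analysis file onwards. It cannot protect choices already built into that file. If a score is voided, corrected or kept by someone who can see the arm, the same anomaly may be treated differently in different arms without any intent, and the blinded analyst receives the result as data.

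The team's knowledge of participants also differs by arm. Under Section 10.1 the guided arm has weekly two-way SMS sessions with research staff, while the other two arms have no human contact beyond technical support. Staff may therefore know more about one arm's participants when judging an odd record. At stake is the credibility of the comparison on the PHQ-A that the masking in Section 7 is meant to secure.

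**Working it through.** No figure in the protocol bears on this point, so there is nothing to recompute. The check is a reading of who does what, and in what order.

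1. **Who can see the arm.** Section 7 names the chief investigators, trial manager and research assistants as unblinded. The paragraph's title and its last sentence also cover research officers, so the Senior Research Officer in Section 10 is reasonably read as one of this group.

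2. **Who cleans.** Section 7 gives cleaning to the whole group. Section 10 gives it to the Trial Manager and Senior Research Officer. The two descriptions differ in breadth, but on either reading the cleaners are unblinded.

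3. **Order of steps.** In Section 10, cleaning and masking are one preparatory task done by the same two people, and transfer to the statistician follows. The protocol nowhere says that cleaning is done on a file without the condition field, or that the file is frozen before the arm code is attached.

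4. **What is settled by rule.**
   - Appendix J's range and date checks apply to every variable, and its 50% threshold is the same in each arm.
   - Section 10 places the duplicate checks in the online assessments, to "check for duplicate users at baseline (e.g., emails, and mobile number checks"). Sections 7 and 10 put randomisation after baseline completion, so no arm exists when these checks run.

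5. **What is left to judgement.**
   - Appendix J says illegal values and incoherent dates will be looked for, but not how a failing record is resolved.
   - Its heading refers to spurious data, but the text does not say what makes a record spurious or what then happens to it.
   - A partial scale must meet the 50% threshold and also still give a valid score. The second condition is not defined.

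6. **Whether removing the condition field alone is enough.** Section 10 says app-use data are downloaded from the same system and linked by participant code. Section 7 accepts that completion data reveal the arm, because it unblinds the statistician when those data are examined. Usage fields and support logs are therefore allocation markers too.

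Steps 1 to 3 establish that cleaning falls outside the blinding. Steps 4 and 5 show that the discretion exposed is real but narrow.

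**The case against.** The strongest reply is that little is left to decide, and much of it stands. Outcomes are self-reported and captured online, so these staff do not rate anyone. The checks in Appendix J are largely arm-neutral. Section 10 fixes intention to treat for everyone randomised, which gives cleaners no licence to drop participants. Section 15 requires corrections to the case report form to be dated, initialled, explained where necessary and traceable. The CONSORT diagram and attrition analyses could help reveal uneven losses.

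These safeguards narrow the gap without closing it. Intention to treat keeps participants in the analysis but does not settle whether a given score is kept or set to missing. An audit trail records a change, but not whether the same choice would have been made in another arm.

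It can also be said that cleaning rules belong in a statistical analysis plan or data-management plan, neither of which is at hand. That is fair, and missing detail is not the point here. The point is that the protocol itself assigns cleaning to unblinded staff ahead of masking.

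A reader might infer three stronger things that the document does not support:

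- **That suspected duplicate accounts are judged with the arm visible.** The only duplicate checks described are at baseline, before randomisation.
- **That those who deliver support and safety calls all clean the data.** Section 10.1 has research assistants run the SMS sessions, and Section 11.1 has the Clinical Psychologist make the calls, arranged by the Trial Manager. Only the Trial Manager's overlap with the safety-call process is explicit. Overlap with SMS support rests on Section 7's broad wording.
- **That the bias can be sized.** Supposing that 5% of one arm's records shift by 1 SD gives 0.05 × 1 = 0.05 SD. Against the planned differences in Section 8, that is 0.05/(0.35 − 0.10) = 20% for self-directed versus control, or 0.05/(0.65 − 0.10) = about 9% for guided versus control. Neither the 5% nor the 1 SD comes from the protocol, so neither percentage is an estimate.

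**Conclusion.** The point holds in a limited form. By the protocol's own procedure, unblinded staff clean the outcome file and mask it, so the statistician's blinding starts one step too late. The decisions exposed are how illegal, incoherent or spurious records are resolved and when a partial scale counts as valid. Direction and size of any effect cannot be derived from the document, and nothing in it shows that bias will occur.

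This is a cheap improvement, not a threat to the trial's validity. The conclusion assumes that the Senior Research Officer belongs to the unblinded group in Section 7, and that no document outside the protocol already requires masked cleaning. If one does, Sections 7 and 10 need only be brought into line with it.

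**What to change.** Amend Sections 7 and 10 so that:

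- outcome data are exported from the Research Engine without the condition, support-log and app-use fields;
- cleaning is done on that file, with every change logged;
- the cleaned file is frozen with a date, and only then merged with the A/B/C code and passed to the statistician;
- both sections name the same roles as responsible for cleaning.

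The same staff can do this. The cost is one extra export and merge step. The protection is incomplete, because staff may still recognise some individual participants from their contact with them. The change log lets a later reader examine any such decision.

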This sample size is sufficient to meet the research aims and answer the research questions because the power calculation reveals that this sample size will allow for statistically significant results. As this trial will be conducted entirely online via the Black Dog Institute Research Engine, no specific trial sites will be established.

9. Selection and Withdrawal of Subjects

All inclusion and exclusion criteria will be assessed through a self-report screening assessment hosted on the study website. Excluded participants will be provided with a generic message and details on youth mental health services and other trusted mental health organisations. Participants will be provided with information on where to seek help and self-care activities. More information on the screening protocol is outlined in Section 9.4 and Appendix A.

To mitigate the potential of participants “gaming” the inclusion criteria (i.e., making multiple attempts to enter the study by various combinations of the inclusion/exclusion criteria), the Participant Information Statement and Consent Form (PISCF) will not stipulate the exact details of the inclusion and exclusion criteria for depressive scores, and will instead give generalised indications.

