Primary analyses will be conducted to determine the effect of the interventions on depressive symptoms at the primary and secondary endpoints. Analyses will be undertaken on an intention-to-treat basis, including all participants randomised, regardless of intervention received. The effectiveness of the trial interventions will be established by a change on the PHQ-9-A between baseline and 6-weeks post-baseline (primary endpoint) and 4-month follow-up (secondary endpoint), based on the interaction between time and condition, using mixed-effects linear modelling with an unadjusted p value of 0.05. Effect sizes will be calculated based on differences in change scores between baseline and 6-weeks post-baseline, using standard deviations of the change scores pooled across conditions. This modelling will account for all available data, under the missing at random assumption. However, attrition analyses will be conducted to determine whether missing data is associated with any baseline demographics (age, gender), mental health status (symptom severity) or other descriptive variables. Any baseline variables identified as substantially imbalanced between groups will be added to the models on an exploratory basis to confirm the robustness of the findings to this imbalance. Where distributional assumptions cannot be satisfied, other modelling may be used to confirm the robustness of the findings. Similar models will be used for secondary outcomes. To analyse the effects of adherence on outcomes, the mixed-effects repeated measures linear modelling will be repeated using the categorical adherence measure as a between group factor (adheres v non-adheres v control). These results will be published in the primary outcomes paper. Exploratory analyses will examine evidence for moderation, that is, whether the intervention was more effective for certain subgroups of the sample. Further, exploratory analyses will also examine evidence for mediation, that is whether the effects of the intervention were driven by other variables.

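### On the effect sizes stated in Section 8, self-directed ClearlyMe versus control has about 52% power, not 80%, unless an unstated baseline correlation near 0.7 is assumed

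*Protocol*

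**What the plan says.** Protocol Section 8 states: "The total baseline sample size required for detecting change in the primary outcome is 489". The listing gives "Trial Arm 1=163 participants" and the same number for the other two arms. The stated basis is: "This is based on calculations using $\alpha=0.05$, power=0.8". To this the section adds an allowance of 20% for participants lost by six weeks, and these planning effects: "small to medium effect sizes for psychoeducation ($d=0.10$), self-directed CBT ($d=0.35$), and guided CBT ($d=0.65$) on depressive outcomes at primary endpoint". The section names no contrast to which the 80% applies, does not say whether the test is two-sided, and does not say in what units d is measured.

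The same section then calls the sample sufficient for the aims and research questions because "the power calculation reveals that this sample size will allow for statistically significant results".

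H1 in Section 4 predicts a larger fall in depressive symptoms for ClearlyMe, covering self-directed and guided use, than for the control. Section 10.1 identifies the control as the psychoeducation arm, which Section 8 credits with d = 0.10. The analysis text in Section 10 tests the time-by-condition interaction "using mixed-effects linear modelling with an unadjusted p value of 0.05", and reports effect sizes "using standard deviations of the change scores pooled across conditions".

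**The concern.** Section 8 lists one effect for each arm, and the control has one of its own. A comparison with control therefore rests on the difference between two listed effects: 0.25 for self-directed and 0.55 for guided. The planned N instead fits 0.35, the self-directed effect taken alone.

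The primary research question and H1 both name self-directed use. If its comparison with control has about an even chance of success on the plan's own assumptions, the 80% figure misinforms anyone who relies on it. A non-significant self-directed result could then be taken as a negative finding from an adequately powered trial, when it would be inconclusive.

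**Working it through.** **Inputs.** From Section 8: alpha 0.05, power 0.80, attrition 20%, arm effects 0.10, 0.35 and 0.65, and 163 per arm. From Section 10: no multiplicity adjustment. Assumed, because not stated: a two-sided test, and d in SD units of the analysed variable (SD = 1).

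**Step 1: reproduce the plan's figure.** By the normal approximation, n per arm = 2(1.960 + 0.842)² / d². For d = 0.35 this is 15.70 / 0.1225 = 128.2, so 129. The exact t-test gives 129.1, so 130. Then 130 / 0.80 = 162.5, so 163, and 3 × 163 = 489. This is an exact match.

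**Step 2: try the other contrasts and tests.** Per arm after dividing by 0.80 (normal approximation):
- d = 0.25: 315 two-sided, 248 one-sided
- d = 0.30: 219 two-sided, 173 one-sided
- d = 0.55: 65 two-sided
- d = 0.35: 127 one-sided; 195 two-sided with a Bonferroni correction for two tests

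An omnibus three-group F test on 0.10/0.35/0.65 (f = 0.225) needs only about 194 evaluable in total. None of these gives 163.

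**Step 3: power at the planned size.** Evaluable per arm: 163 × 0.80 = 130.4, about 130. Power is approximately Φ(d√(n/2) - 1.960). For 0.25: 0.25 × √65 = 2.016, and Φ(0.056) = 52.2%; the t-test gives 51.9%.

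| Test | Difference | Power |
|---|---|---|
| Self-directed vs control | 0.35 - 0.10 = 0.25 | 52% |
| Guided vs self-directed | 0.65 - 0.35 = 0.30 | 67% |
| Guided vs control | 0.65 - 0.10 = 0.55 | 99% |
| Both ClearlyMe arms pooled (260) vs control (130) | 0.50 - 0.10 = 0.40 | 96% |
| Three-arm omnibus, 390 evaluable | f = 0.225 | 98% |

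For 0.25, a one-sided test gives 64%. With no attrition at all, 163 per arm gives 61% two-sided. For 80% power at 0.25, the t-test needs 253 evaluable per arm; 253 / 0.80 = 316.25, so 317 randomised per arm and 951 in total.

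**Step 4: vary the units of d.** If d is in endpoint-score SD units and baseline is a covariate, the residual SD is √(1 - r²), where r is the baseline-to-6-week correlation. The protocol gives no r, so the values are assumptions. Power for 0.25 at 130 per arm:

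| r | Baseline-adjusted | Simple change score |
|---|---|---|
| 0.3 | 56% | 40% |
| 0.5 | 64% | 52% |
| 0.6 | 71% | 61% |
| 0.7 | 80% | 74% |

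At r = 0.70, 0.25 / √(1 - 0.49) = 0.350, which leads again to 130, 163 and 489. If d is in change-score SD units, a test of change has 52% power whatever r is.

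**The case against.** The arithmetic above is not in dispute; what may be concluded from it is.

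- **Derivation.** A reader might infer that 163 can arise only by ignoring the control's 0.10, or that the sponsor forgot to subtract it. The documents do not support that. A difference of 0.25 with baseline adjustment and r = 0.70 gives exactly the same 163, so N alone cannot tell the two routes apart. What stands is that the protocol states no correlation.
- **Units.** The change-score SD in Section 10 defines how effects will be reported. Section 8 places its planning effects at the primary endpoint, which can be read as endpoint-score SDs. The 52% is therefore conditional on the units, and a range is needed. This objection stands.
- **Contrast.** H1 does not say that each ClearlyMe arm is tested separately. It can be read as the pooled arms, and Section 10 describes one time-by-condition interaction. Those tests have 96% and 98% power. This stands as a limit on scope, but neither test yields 163, and Section 8 declares the sample sufficient for research questions that name self-directed use.
- **Meaning of 0.35.** It might already be a difference from psychoeducation, in which case power is 80%. But psychoeducation's 0.10 stands in the same list and would then have no role.

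The mixed model's use of partial data does not close the gap, since even complete follow-up gives only 61% in change-score units.

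**Conclusion.** On the stated inputs, Section 8's N fits a difference of 0.35 from zero, not the 0.25 between self-directed ClearlyMe and the control. Power for that contrast is about 52%, assuming a two-sided 5% test, 130 evaluable per arm and d in change-score SD units. With d in endpoint-score SD units and baseline adjustment it runs from 56% to 80% as r goes from 0.3 to 0.7. Within that range only r of about 0.7, which the protocol does not state, restores 80%.

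A reader might go further and call the whole trial underpowered. That does not follow: guided versus control, the pooled contrast and the omnibus test all exceed 95% on the plan's own effects. The shortfall concerns self-directed versus control and, to a lesser degree, guided versus self-directed (67%). If H1 were taken to require both ClearlyMe arms to beat control, the chance that both succeed is also about 52% (simulation, change-score units), because the self-directed contrast is the limiting one.

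The protocol also plans no reading of a non-significant result as proof of no effect. That is a risk created by the power statement, not something the protocol says. The claim that the sample will permit significant results is unsupported in any case, since no sample size ensures significance.

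**What to change.** Keep 489. In Section 8:

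- Name the contrast that sets N, and state the sidedness of the test and the units of d.
- Replace the single 80% figure with power per contrast at 130 evaluable per arm: self-directed versus control about 52% (or the figure for a stated and justified correlation, with the range above), guided versus control 99%, guided versus self-directed 67%.
- State that 0.35 is the smallest between-arm difference detectable with 80% power in change-score SD units.
- Delete the claim that "the power calculation reveals that this sample size will allow for statistically significant results".
- Add that a non-significant self-directed versus control result will be interpreted by its confidence interval.
- If a between-arm difference of 0.35 or a correlation near 0.7 was in fact assumed, state and justify it in the same edit.

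The cost is protocol wording and a less favourable stated power for one contrast. Recruitment, randomisation and analysis are unchanged.
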